Date: 1 March 2020

Study Name: Comparison Of The Incidence Of Recurrent Laryngeal Injury Following The Dissection Of The Nerve By Cranio-Caudal And Lateral Approach By Using Introoperative Nerve Monitoring

Study Design: This prospective study was approved by the institutional review board and informed consent was obtained from each patient . A total of 327 patients who were referred to undergo thyroid surgery between June 2018 and November 2019 were assessed for the eligibility to participate in the study. Of these, 233 were considered to be eligible for the study. Exclusion criteria included previous thyroid or parathyroid surgery, substernal goiter, preoperative VCP, evidence of lateral lymph node metastasis, intentional transection of the RLN due to tumor invasion, failure to assess RLN functioning due to equipment issues with the IONM setup, presurgical dissection amplitude of $<500\mu\text{V}$ and patient's refusal to participate in the study. Of 327 patients, 94 were excluded preoperatively due to previous neck surgery (n=47), evidence of lateral neck metastasis(n=24), patient's refusal (n=13) and presence of substernal goiter (n=10). The remaining 233 patients were randomized to have RLN's identified by lateral (n=121) or cranio-caudal approach (n=112 (Figure 1). Computer generated random numbers were generated and printed on cards. These cards were placed in sealed, opaque envelopes. On the morning of operation, one envelope was opened before the operation and, depending of the parity of the number, RLN's of the patient were dissected either by cranio-caudal or lateral dissection during the operation. The patients and the nerves at risk (NAR's) in the lateral and cranio-caudal approach groups were classified as group 1 and 2, respectively. In group 1 and 2, nine and twenty-six patients were further excluded, respectively, owing to intraoperative failure to assess RLN functioning due to equipment issues with the IONM setup or presurgical dissection amplitude of $<500\mu\text{V}$.

Thus, the data of 198 patients were analysed for primary and secondary outcome measures. The primary endpoint was RLN injury and the secondary endpoints included the effect of clinicopathological features, anatomic variations and adverse EMG changes on the occurrence of RLN injury. Of 198 patients, 112 were in the lateral approach group (group 1) and 86 in the cranio-caudal approach group (group 2). Total thyroidectomy or lobectomy was

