performed in 158 (79.8%) and 40 (20.2%) patients, respectively. Sixteen (8%) patients underwent unilateral central lymph node dissection (CLND) additional to total thyroidectomy. Age, gender, body mass index (BMI), the indications for surgery, presence of hyperthyroidism, evidence of autoimmune thyroid disease (ATD) and thyroid lobe volume were recorded in all patients, preoperatively. Thyroid lobe volume was calculated by using the dimensions (length(L), width(W), thickness(T)) of each thyroid lobe measured by ultrasonography according to the following formula; $\pi/6 \times L \times W \times T^{18}$.

All NAR's were dissected by using CIONM including vagal response evaluation at the beginning and at the end of the operation (IONM = L1,V1, R1, R2,V2, L2) according to the recommendations by the International Intraoperative Neural Monitoring Study Group ⁷. All patients underwent pre-, and postoperative laryngoscopic examination within 2 days after surgery, and repeated serially if abnormal (L1, L2). All operations were performed by experienced endocrine surgeons. Length of RLN dissection was defined as extended if the nerve was dissected for 5 cm or greater. Duration of lobectomy for each site, period of time for initial identification of RLN after the mobilization of upper pole on each site, the relationship of the RLN to the ligament of Berry (LOB) and to the Tubercl of Zuckerkandl (TZ) (if present), extralaryngeal branching of the RLN, length of RLN dissection, presurgery and postsurgery amplitude and latency of the vagus and the RLN, occurrence of adverse EMG changes and recovery time or loss of signal (LOS) were recorded intraoperatively in all patients. Serum levels of calcium and parathormone on the first postoperative day were analyzed in all patients. The rates of post-thyroidectomy hypoparathyroidism and vocal cord palsy (VCP) were recorded. Final histopathological diagnosis was documented in all patients, postoperatively.

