The baselines for latency and amplitude were automatically calibrated after the connection of the vagus electrode with the neuromonitoring system. CIONM had been carried out with one of the two following commercially available neuromonitoring devices: (1) NIM 3.0 Nerve Monitoring Systems; Medtronic Xomed, Jacksonville, FL; or (2) [name] GmbH, Avalanche SI, Germany. Achievement of initial presurgical dissection amplitude of $\geq 500\mu\text{V}$ was aimed in all patients. During the operations, adverse EMG parameters were defined as amplitude decrease of 50% or more of baseline value and/or latency increase of 10% or more ¹¹. A combined event (CE) was defined as concordant amplitude decrease of more than 50% and latency increase of more than 10%, regarding to baseline values ¹¹. The surgical maneuver was immediately altered and the traction released if adverse EMG changes were noted during surgery and waited to achieve the recovery of EMG changes. Recovery was defined as amplitude recovery to $>50\%$ of the initial baseline amplitude. Loss of signal (LOS) was defined as amplitude $<100\mu\text{V}$ ¹⁹. In case of LOS during the surgery of initial site, contralateral surgery was aborted if the amplitude did not recover to greater than 50% of the initial baseline amplitude within 20 minutes of the initial decline. During surgery, isthmus was divided first in both group of patients. Then the upper lobe of the gland was dissected through the avascular zone between the upper lobe and the cricothyroid muscle. The external branch of the superior laryngeal nerve was identified visually and, or by using neuro-monitoring hand probe prior to dissection of the upper pole vessels, and then the branches of upper pole vessels were ligated individually. Identification and preservation of all parathyroid glands and their vascular supply was tried in all cases. In case of incidental parathyroidectomy or totally compromised vascularity of the parathyroid glands, autotransplantation in to sternocleidomastoid muscle was performed.

RLN identification

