Date: 1 March 2020

Study Name: Comparison Of The Incidence Of Recurrent Laryngeal Injury Following The Dissection Of The Nerve By Cranio-Caudal And Lateral Approach By Using Introperative Nerve Monitoring

Statistical Analysis Plan: The Statistical Package for Social Sciences (SPSS) for Windows Version 21.0 (Armonk, NY: IBM Corp.) was used for statistical analysis. The continuous variables are summarised as mean \pm standard deviation. The differences between the groups were assessed using the Student's t-test and a Mann-Whitney U test for normally distributed and non-normally distributed data, respectively. Univariate analysis by Chi-square test was performed to test differences in proportions. Statistically significant results obtained from the univariate analysis were subjected to multivariate logistic regression. A p value <0.05 was considered to be statistically significant.

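### Extent of surgery is reported only as performed, so a total thyroidectomy aborted after first-side loss of signal would count as a lobectomy; if extent is analysed as a factor for RLN injury, this creates a spurious excess in the lobectomy group

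*Protocol*

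**What the plan says.** The protocol, under Thyroid surgery and CIONM technique, sets the rule for stopping after the first side. "Loss of signal (LOS) was defined as amplitude" below 100 µV, and when this happens on the first side, "contralateral surgery was aborted if the amplitude did not recover to greater than 50% of the initial baseline amplitude within 20 minutes of the initial" fall.

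Extent of surgery appears once, in the Study Design text. After giving 112 and 86 analysed patients in the two groups, it reports total thyroidectomy and lobectomy as "performed in 158 (79.8%) and 40 (20.2%) patients, respectively". There is no third category for operations stopped after one side. Planned extent is not among the items listed as recorded. The number of aborted second sides is not given, and no rule says how such patients are classified.

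On endpoints, the same section says: "The primary endpoint was RLN injury and the secondary endpoints included the effect of clinicopathological features, anatomic variations and adverse EMG changes". The SAP then says: "Statistically significant results obtained from the univariate analysis were subjected to multivariate logistic regression". It names no candidate covariates and mentions neither planned extent nor the abort rule.

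**The concern.** A patient listed for total thyroidectomy who loses signal on the first side without recovery leaves the theatre with one lobe removed. If extent means what was done, that patient is a lobectomy, and is one because of the nerve event. Performed extent is then partly a consequence of the outcome that the analysis sets out to explain.

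This matters if extent is treated as a clinicopathological feature, which the open wording of the secondary endpoint allows. Injured patients are taken out of the large total-thyroidectomy group and put into a group of only 40, where a few cases change the rate noticeably. If the association passes the univariate screen, the logistic model adjusts its other coefficients for a variable determined after the injury.

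**Working it through.** **The plan's own figures.** 158 + 40 = 198; 158/198 = 79.8%; 40/198 = 20.2%. The two categories account for every analysed patient, so any aborted case sits in one of them.

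**Assumptions (not in the documents).** Every nerve has the same injury risk p, so extent has no true effect per nerve. A share s of first-side injuries comes with unrecovered LOS and triggers the abort. Aborted cases count as injured and are filed as lobectomies. I take p from 2% to 5% and s from 50% to 100%.

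**Formulas, holding the performed counts at 158 and 40.**
- Aborted totals among the lobectomies: a = 158ps/(1 − ps).
- Expected injuries among the 40: a + p(40 − a).
- First-side risk in completed totals: f = p(1 − s)/(1 − ps).
- Patient-level risk in completed totals: 1 − (1 − f)(1 − p).

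**Example, p = 3%, s = 100%.** a = 158 × 0.03/0.97 = 4.9. Lobectomy injuries = 4.9 + 0.03 × 35.1 = 5.9, or 14.9% of 40. In completed totals f = 0, so the risk is 3.0%, or 4.7 of 158.

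**Results.** The p-values are uncorrected chi-square on rounded expected counts.

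| p | s | aborted among 40 | lobectomy risk | total risk | counts | chi-square p |
|---|---|---|---|---|---|---|
| 2% | 50% | 1.6 | 5.9% | 3.0% | 2/40 v 5/158 | 0.57 |
| 3% | 50% | 2.4 | 8.8% | 4.5% | 4/40 v 7/158 | 0.17 |
| 5% | 50% | 4.1 | 14.6% | 7.4% | 6/40 v 12/158 | 0.15 |
| 2% | 100% | 3.2 | 9.9% | 2.0% | 4/40 v 3/158 | 0.013 |
| 3% | 100% | 4.9 | 14.9% | 3.0% | 6/40 v 5/158 | 0.0035 |
| 5% | 100% | 8.3 | 24.7% | 5.0% | 10/40 v 8/158 | 0.00009 |

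The smallest expected cell is between 1.4 and 3.6. Fisher's exact test on the three rows with s = 100% gives 0.032, 0.010 and 0.0005.

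**Simulation over the same range (3,000 trials per scenario).** Performed extent produced a false odds ratio for lobectomy of 2.0 to 6.2 per patient and 4.1 to 12.8 per nerve. A falsely significant excess after lobectomy appeared in 17% to 95% of trials per patient and 46% to 99.5% per nerve. With extent classified as planned, the per-nerve odds ratio was 1.00 and a false excess after lobectomy appeared in about 4% to 5% of trials. When only 60% to 80% of unrecovered LOS counted as injury, the expected odds ratios hardly moved.

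**Effect on the comparison of arms.** A planned total thyroidectomy has expected injuries p + (1 − ps)p and expected nerves operated 1 + (1 − ps). The ratio is p(2 − ps)/(2 − ps) = p for every p and s. At p = 5%, s = 100%: 0.0975/1.95 = 5%. Fewer second nerves are exposed, but expected injuries fall in the same proportion.

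**The case against.** The strongest reply is that no stated analysis is shown to be wrong. Extent is not named as a candidate factor. It is absent from the list of variables compared between groups and from the planned correlations, and the 158/40 split is given as description. No passage says that an aborted total was counted as a lobectomy, and the number of aborts could be zero. The trigger is also narrower than RLN injury in general: it needs LOS on the first side and then failure to recover within the time limit. All of this stands, and it makes the concern conditional. It does not remove it, because the secondary endpoint is open-ended, the SAP lists no covariates, and the two extent categories leave no other place for an aborted case.

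The size is also open to challenge. Significance at patient level depends on s: at 50% none of the expected tables reaches p < 0.05. That stands too, so one cannot say that extent would pass the screen, only that it could.

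Two stronger readings are tempting. One is that the lost second nerves bias nerve-level rates by arm. Under equal risk per nerve they do not, as the last step of the working shows. The other is that the true direction of effect is reversed, since at 3% per nerve a planned total carries 1 − 0.97² = 5.9% patient-level risk against 3% for a planned lobectomy. That ordering only reflects two nerves against one. Per nerve the true effect in this model is null, so the error is a spurious association, not a reversal.

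Finally, LOS and recovery time were recorded intraoperatively, so much of what is needed to find the aborted cases already exists. That stands, and it makes the fix cheap.

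**Conclusion.** The point holds in conditional form. On the literal wording, performed extent depends partly on the outcome, and using it as a risk factor or covariate for RLN injury would make lobectomy look spuriously harmful. With 2% to 5% risk per nerve and 50% to 100% of first-side injuries triggering the abort, about 2 to 8 of the 40 lobectomies would be aborted totals. The false patient-level contrast would run from about 6% against 3% to about 25% against 5%. Whether it reaches significance depends on inputs that the documents do not give.

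A reader might infer that the randomised comparison of nerve injury is compromised, or that lobectomy was in fact reported as a risk factor. The documents support neither. The concern is confined to analyses that use extent of surgery.

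**What to change.** 1. In any test or regression that uses extent, classify it by the operation planned before incision. Identify aborted cases from the recorded LOS and recovery data together with the operative list.
2. State in the SAP that performed extent will not be used as a risk factor or covariate for RLN injury.
3. Report the number of aborted second sides by allocated arm. If there were none, one sentence saying so closes the point.

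The cost is a short chart check, one added line in a table, and a slightly smaller lobectomy group. A comparison restricted to the first-operated side is optional and is not needed to correct the per-nerve comparison of arms; among the 2 × 158 + 40 = 356 nerves operated, it would set aside 158. The clinical abort rule is left as it is.

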Date: 1 March 2020

Study Name: Comparison Of The Incidence Of Recurrent Laryngeal Injury Following The Dissection Of The Nerve By Cranio-Caudal And Lateral Approach By Using Introperative Nerve Monitoring

Statistical Analysis Plan: The Statistical Package for Social Sciences (SPSS) for Windows Version 21.0 (Armonk, NY: IBM Corp.) was used for statistical analysis. The continuous variables are summarised as mean \pm standard deviation. The differences between the groups were assessed using the Student's t-test and a Mann-Whitney U test for normally distributed and non-normally distributed data, respectively. Univariate analysis by Chi-square test was performed to test differences in proportions. Statistically significant results obtained from the univariate analysis were subjected to multivariate logistic regression. A p value <0.05 was considered to be statistically significant.

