Demographic data, BMI, the indications for surgery, clinicopathological features, thyroid volume, duration of the operation, period of time for RLN identification, anatomical variations, length of RLN dissection, presurgery and postsurgery amplitude and latency of the vagus and RLN, the rate of adverse EMG changes, LOS and morbidity (vocal cord palsy, hypoparathyroidism) were compared between group 1 and 2. The correlation between intraoperative adverse EMG changes and anatomic variations, lobe volume and type of thyroid disease was investigated as well.

Thyroid surgery and CIONM technique

All operations were performed under general anesthesia by using a small dose (0.3 mg/kg) of non-depolarizing muscle relaxant (Esmeron; MSD Sharp & Dohme GmbH, Haar, Germany) at intubation. The endotracheal tube was properly inserted to ensure that the recording surface electrode was placed at the level of the vocal cords. Prior to lobectomy, the carotid sheath was carefully dissected and the vagus nerve was identified using a hand held stimulation probe. The vagus nerve was dissected over a distance of ≤ 1 cm to place the vagus electrode. (automated periodic stimulation (APS) (Medtronic Xomed, Jacksonville, FL) or saxaphone probe (vagus electrode) ([name] GmbH, Avalanche SI, Germany).

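### Continuous variables tested by ranks are still summarised as mean and SD, and Student's t is named without an unequal-variance version: a minor, near-free fix outside the primary analysis

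*SAP*

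**What the plan says.** The SAP is a single paragraph. On summaries it says "The continuous variables are summarised as mean" with standard deviation, for all continuous variables alike. On tests it says "The differences between the groups were assessed using the Student's t-test and a Mann-Whitney U test for normally distributed and non-normally distributed data, respectively", and on the threshold "A p value <0.05 was considered to be statistically significant". It mentions no median or interquartile range, no effect estimate or confidence interval for a continuous comparison, and no unequal-variance t-test. It does not say how normality is judged or which variable gets which test.

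The Protocol, in the paragraph before the heading on thyroid surgery and CIONM technique, lists what is compared between the arms. The continuous items include BMI, thyroid volume, operation duration, time to nerve identification, length of dissection, and "presurgery and postsurgery amplitude and latency of the vagus and RLN".

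On numbers, the Protocol (Study Design) says "Of 198 patients, 112 were in the lateral approach group (group 1) and 86 in the cranio-caudal approach group (group 2". On the outcome it says "The primary endpoint was RLN injury".

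**The concern.** There are two separate weaknesses.

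**Summary and test do not match.** Times and volumes cannot fall below zero, and baseline amplitude is cut off below because patients under 500 µV were excluded. Right skew is plausible for these variables. The mean is pulled by the upper tail and the Mann-Whitney test largely is not. If one technique is usually quicker but occasionally very slow, the rank test can favour it while the printed means favour the other. With no effect estimate or interval specified, the reader has nothing to settle the conflict.

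**Student's t pools the variances.** With unequal arms, pooling gives the wrong standard error when the SDs also differ. The two techniques follow different dissection sequences (Protocol, RLN identification), so equal spread in procedure-related measurements cannot be taken for granted.

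At stake is how far baseline and secondary continuous comparisons can be trusted and read.

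**Working it through.** The plan has no sample-size, power or SD figure to reproduce on this point. I checked the patient flow first and then each weakness.

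**Arm sizes (Protocol, Study Design).** The randomized numbers are given as "The remaining 233 patients were randomized to have RLN's identified by lateral (n=121) or cranio-caudal approach (n=112", and then "In group 1 and 2, nine and twenty-six patients were further excluded, respectively".
- 327 − 94 = 233 = 121 + 112
- 121 − 9 = 112 lateral; 112 − 26 = 86 cranio-caudal; total 198
- Ratio 112/86 = 1.30

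**Student's t at 112 and 86.** I assume a two-sided 0.05, since the SAP does not state sidedness. The SD ratios are also assumptions. The large-sample true error is

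2 × [1 − Φ(1.96 / r)], with r² = (s₁²/n₁ + s₂²/n₂) / [s_p² (1/n₁ + 1/n₂)].

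Worked case, cranio-caudal SD 1.5 times the lateral SD:
- s₁²/n₁ + s₂²/n₂ = 1/112 + 2.25/86 = 0.03509
- s_p² = (111 × 1 + 85 × 2.25)/196 = 1.542
- 1/n₁ + 1/n₂ = 0.02056
- r² = 0.03509 / (1.542 × 0.02056) = 1.107, so r = 1.052
- Error = 2 × [1 − Φ(1.863)] = 0.0625

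Simulation with normal data, 100,000 replicates per row:

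| SD lateral : cranio-caudal | Formula | Student | Welch |
|---|---|---|---|
| 1 : 1 | 0.050 | 0.049 | 0.049 |
| 1 : 1.25 | 0.057 | 0.057 | 0.050 |
| 1 : 1.5 | 0.063 | 0.063 | 0.050 |
| 1 : 2 | 0.070 | 0.069 | 0.049 |
| 1.25 : 1 | 0.044 | 0.044 | 0.050 |
| 1.5 : 1 | 0.039 | 0.039 | 0.049 |
| 2 : 1 | 0.034 | 0.036 | 0.051 |

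At a ratio of 3, which is extreme, Student gives 0.079 or 0.030 and Welch 0.050. With equal arms (99 and 99), Student stays at 0.049 to 0.052 for every ratio. Distortion therefore needs unequal arms and unequal SDs together.

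**Means against Mann-Whitney at 112 and 86.** For a log-normal variable, mean/median = exp(s²/2), where s is the log-SD. That is exp(0.125) = 1.13 at s = 0.5 and exp(0.5) = 1.65 at s = 1.0. In 5,000 simulated trials per row:

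| Log-SD, arm 1 / arm 2 | Medians | True means | Significant | Significant with sample means in opposite order | As share of significant |
|---|---|---|---|---|---|
| 0.5 / 1.0 | 1.455 / 1.000 | 1.649 / 1.649 | 87.2% | 34.9% | 34.9/87.2 = 40% |
| 0.5 / 1.0 | 1.000 / 0.741 | 1.133 / 1.221 | 71.3% | 39.0% | 39.0/71.3 = 55% |
| 0.5 / 0.8 | 1.000 / 0.819 | 1.133 / 1.127 | 52.5% | 9.2% | 9.2/52.5 = 18% |
| 0.5 / 0.5 | 1.000 / 1.350 | 1.133 / 1.530 | 98.0% | 0% | 0% |

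The result depends on the median ratio as well as on spread. With log-SDs of 0.95 and 0.6, the share of significant results that conflict is about 44% at a median ratio of 0.9, 31% to 34% at 0.8, 16% at 0.7, 3% at 0.6 and 0.3% at 0.5. With log-SDs of 0.7 and 0.6 it is below 1%, and with equal log-SDs it is 0%.

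**Unit of measurement.** The counts 112 and 86 are patients. Lobe volume, identification time and nerve signals are recorded per side or nerve. The stated procedures give 158 × 2 + 40 = 356 sides, and their split by arm is not given. The t-test figures above therefore apply as computed only to variables with one value per patient.

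**The case against.** The strongest reply is that little follows from this, and much of that stands.

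- A reader might infer that the t-test error rate is wrong simply because the arms are unequal. The documents do not support that. With equal SDs the error at 112 and 86 is 0.049, and the documents report no SDs.
- Under the SAP's own rule, Student's t is used only for data judged normal. The skewed variables, where large SD ratios are most likely, would go to Mann-Whitney. What remains is variables such as age or BMI. These are measured before surgery in randomized arms, so technique cannot change their spread. Ratios of 2 or 3 are hard to justify there.
- A reader might infer that means and p-values will often conflict. Conflict needs a sizeable difference in spread together with a modest difference in medians, and any single percentage reflects the scenario chosen.
- A reader might infer that a normality test picks the method. The SAP names no such test or criterion, and choosing t or Mann-Whitney by distribution is common practice. What can be said is that the method is not fixed variable by variable.
- Parathormone might be added to the skewed variables. The Protocol records it, but its list of between-arm comparisons names hypoparathyroidism, a proportion.

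The reply does not remove the mismatch itself, which is plain in the SAP's text, or the absence of an unequal-variance test and of any effect estimate with an interval.

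**Conclusion.** The point holds as a minor one. The mismatch between summary and rank test is certain from the SAP's wording. Whether it misleads depends on skewness and spread that the documents do not give: across the scenarios tried, conflicting direction ran from 0% to about 55% of significant results, with none at equal log-SD.

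The t-test weakness is conditional and modest. The error is near 5% with equal SDs, about 4% to 6% at SD ratios up to 1.5, and about 3.5% to 7% at a ratio of 2. It is conservative when the larger SD lies in the lateral arm. These figures assume normal data, a two-sided 5% level and patient-level counts.

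A reader might go further and doubt the main result. That is not supported: RLN injury is not a continuous variable, differences in proportions are tested by chi-square, and this rule does not touch them.

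**What to change.** Amend the SAP in three places.

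1. For variables analysed by ranks, report median and interquartile range, with the Hodges-Lehmann shift and its 95% interval. The shift matters as well as the median: it is the estimate that corresponds to the rank test, and medians alone need not agree with that test when the two distributions differ in shape.
2. For variables compared by means, use Welch's t-test with the mean difference and 95% interval. In every scenario run it held 4.9% to 5.1% at 112 and 86, so little is lost by using it throughout.
3. List each continuous variable with its method and its unit (patient, side or nerve). Times and amplitudes can be assigned to ranks or to the log scale. The plan is dated March 2020 and the Protocol of the same date already gives the analysed numbers, so base the assignment on the nature of the measurement and state when it was made.

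The cost is SAP wording and a re-run of the secondary tables, with no new data. Correlation between two sides of one patient is a separate matter that this change does not resolve.

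### Unrestricted logistic regression on significance-screened predictors can give no finite odds ratio for adverse EMG change and inflated odds ratios for the rest, if RLN injuries are few

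*SAP*

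**What the plan says.** The Protocol (Study Design) makes risk factors for injury a secondary objective: "the secondary endpoints included the effect of clinicopathological features, anatomic variations and adverse EMG changes on the occurrence of RLN injury". The same section gives the denominator: "Thus, the data of 198 patients were analysed for primary and secondary outcome measures".

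The SAP describes the analysis in three steps. Screening: "Univariate analysis by Chi-square test was performed to test differences in proportions". Threshold: "A p value <0.05 was considered to be statistically significant". Model: "Statistically significant results obtained from the univariate analysis were subjected to multivariate logistic regression". For software it says "The Statistical Package for Social Sciences (SPSS) for Windows Version 21.0 (Armonk, NY: IBM Corp.) was used for statistical analysis".

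The SAP gives no maximum number of predictors, no covariate list, no penalised or exact estimator, and no rule for empty cells or not-applicable values. As no other estimator is named, I take it to be ordinary maximum likelihood.

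Three Protocol definitions matter. Under Study Design, nerves with a pre-dissection amplitude below 500 µV are excluded. Under the CIONM technique section, an adverse EMG change is an amplitude fall of at least 50% and/or a latency rise of at least 10%, and loss of signal is an amplitude below 100 µV. Under Study Design, the relation of the nerve to the tubercle is recorded for "the Tubercl of Zuckerkandl (TZ) (if present"), with no code stated for nerves that lack one.

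**The concern.** Ordinary logistic regression has two weaknesses when injuries are few. If one level of a predictor holds all or none of the injuries, its odds ratio has no finite estimate, and software prints a very large number with a meaningless interval. If predictors enter because they were significant in the same data, those that enter tend to be the ones whose effect was overestimated by chance.

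At stake is the secondary question of which features raise the risk of nerve injury. The predictor of most interest in a nerve-monitoring study, adverse EMG change, is the one most exposed to the first weakness. Every other predictor that enters is exposed to the second.

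**Working it through.** **Denominators (Protocol, Study Design).** 327 − 94 = 233 randomised. 121 − 9 = 112 and 112 − 26 = 86, and 112 + 86 = 198. This matches the stated figure. With 158 total thyroidectomies and 40 lobectomies, nerves at risk = 2 × 158 + 40 = 356 (derived, not stated).

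**Injuries (assumed).** 10/356 = 2.8% and 18/356 = 5.1%; 10/198 = 5.1% and 16/198 = 8.1%. The wider range considered is 5 to 36 injuries (1.4 to 10.1% of nerves).

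**Parameters that the injuries support.** At 10 injuries per parameter, 10 to 18 injuries allow 1 (5 injuries: 0; 36 injuries: 3). At 5 per parameter, they allow 2 to 3 (5 injuries: 1; 36 injuries: 7).

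**Why adverse EMG change is exposed.** Loss of signal from a baseline of at least 500 µV is a fall of more than 1 − 100/500 = 80%, so it always satisfies the 50% criterion. If a share s of injured nerves shows an adverse change, all e injured nerves show it with probability s^e, and the cell for injured nerves without an adverse change is then empty:
- s = 0.90: 0.9^10 = 35%, 0.9^18 = 15%
- s = 0.95: 0.95^10 = 60%, 0.95^18 = 40%

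**Simulation of the SAP's rule.** Inputs, all assumed except the 356 nerves: 12 binary candidates, four with true odds ratio 2.0 and eight with none; prevalences 4.5 to 60%; an optional adverse-EMG variable present in 8% of uninjured nerves; nerves independent; 3000 data sets per setting. Candidates with chi-square p<0.05 enter a maximum-likelihood model.

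| Adverse EMG in injured nerves | No finite odds ratio, 10 injuries | 18 injuries |
|---|---|---|
| variable not offered | 5.7% | 1.7% |
| 80% | 15% | 3% |
| 90% | 38% | 16% |
| 95% | 64% | 43% |

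A second set-up used four candidates (prevalences 43, 30, 20 and 8%, true odds ratio 2.5), with 198 patients and 10 or 16 injuries, or 356 nerves and 18 injuries. Without EMG, 4%, 0.4% and 0.4% of screened fits fail. With EMG at 80 to 95%, 21 to 63% fail at 10 injuries and 3 to 47% at 16 to 18. Across both set-ups the ranges are about 15 to 64% and 3 to 47%.

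**Inflation (first set-up, geometric mean odds ratio of selected true predictors, truth 2.0).**

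| Estimator | 10 injuries | 18 injuries |
|---|---|---|
| Maximum likelihood, finite fits | 5.6–5.8 | 3.9–4.2 |
| Firth | 5.1–5.2 | 3.7–3.8 |

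With fixed predictors and no screen, a true 2.5 is estimated as 2.54–2.73 by maximum likelihood and 2.45–2.59 by Firth. Most of the inflation therefore comes from selection, and little from the estimator. Chance entry is also likely: with 20 independent null candidates (an illustrative number), at least one passes with probability 1 − 0.95^20 = 64%.

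**The case against.** The best defence is that the screen already does much of the work of a cap. Only about 1.2 to 2.5 predictors enter on average, and most predictors with an empty cell fail the test. That stands, and it rules out several stronger readings.

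- *A reader might infer that a large share of all fits would fail.* If the four predictors of the second set-up are forced into every model, 22%, 7% and 5% of fits have no finite estimate. The SAP does not force them in. Under its own rule these become 4%, 0.4% and 0.4%.
- *A reader might point to central node dissection as the sparse predictor:* "Sixteen (8%) patients underwent unilateral central lymph node dissection (CLND) additional to total thyroidectomy". If those patients have no injuries, the chi-square p is 0.34 with 10 injuries in 198 patients, 0.22 with 16 in 198, and 0.34 with 18 in 356 nerves (taking 16 nerves). It would not enter.
- *A reader might infer that nerves without a tubercle will be deleted.* That needs the tubercle relation to pass the screen and absence to be coded as missing. The documents do not state the coding, and absence may already be a category.

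It can also be said that only a secondary endpoint is affected, since the randomised comparison does not depend on this model, and that both documents are dated after recruitment ended. Both points are right. They limit the weight of the concern and mean that a change would not be prospective.

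The defence fails for adverse EMG change. That variable is so closely tied to injury that it would be expected to pass the screen, empty cell or not. The screen is also the source of the inflation.

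**Conclusion.** The concern holds in this limited form. The SAP's rule leaves the odds ratio for adverse EMG change at substantial risk of being undefined, and it overstates the odds ratios of the other predictors that enter, about two- to threefold for a true value of 2.0.

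The size rests on assumptions. The injury count, the share of injured nerves with adverse EMG change, the prevalences and the true effects are not in the documents. At 18 injuries and 80% the failure rate is only 3%; at 10 injuries and 95% it is 64%. The limit on model size is less sensitive: even 36 injuries support only 3 parameters at 10 injuries each. The simulations treat nerves as independent; two nerves per patient in 158 patients would leave somewhat less information.

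The plan should be changed on this point, for the secondary risk-factor analysis only.

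**What to change.** Replace the univariate screen with a short list of covariates chosen on clinical grounds, without reference to the univariate results. Allow about one parameter per 5 injuries beyond the approach term, counting every level of a categorical variable. Fit by Firth penalised likelihood with profile-likelihood intervals. Both parts are needed: Firth keeps the estimates finite, and the fixed list removes the selection. State the injury count and the unit of analysis beside the model.

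If the tubercle relation is used, code absence of a tubercle as a level so that no nerve is dropped. With two relation categories plus absence this takes two parameters, the whole allowance at 10 injuries, so it must earn its place.

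Because the SAP is dated after recruitment, describe the revised model as specified at that stage.

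Cost: a sentence or two in the SAP and a short run in R or SAS beside SPSS 21. The downside is that fewer risk factors can be examined together; the others can be reported descriptively.
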